1. TRIAL DESIGN

1.1. Type/Design of Trial

This study will be a Phase II, open label, single arm, multicenter pilot study in subjects with homozygous familial hypercholesterolemia. Informed consent (and written assent if subject is < 18 years of age) will be obtained from subjects before the initiation of any study-specific procedures.

Subjects who meet study inclusion/exclusion criteria will be instructed to continue to follow a National Cholesterol Education Program (NCEP) Adult Treatment Panel III (or comparable) diet [Appendix C in protocol] and will be required to maintain their current lipid lowering drug therapy for the duration of the study.

In this study, 8-10 subjects will be enrolled and receive open label inclisiran 300mg SC. Dosing interval will be determined by PCSK9 level at Day 60 or 90 or rate of change of PCSK9 levels between Days 60 and 90.

On Day 1, eligible subjects will be enrolled and receive the first SC administration of inclisiran. After first study drug administration, the subject will be observed in the clinic for at least 4 hours post injection before being discharged. Subjects will return at Day 14 and Day 30 and then at monthly intervals. If a second dose of study drug is deemed necessary (if mean serum PCSK9 levels are not suppressed by > 70% at Day 60 or 90, as compared to baseline), subjects will receive this dose at Day 90 or 104 respectively, based on PCSK9 levels from the previous visit.

Study visits will include collection of AE and SAE data, vital signs, ECGs, concomitant medication, and laboratory tests. The study also includes collection of biomarker samples and, where approved by the independent ethics committee and/or institutional review board (IEC/IRB) and applicable regulatory and other authorities, all subjects will be invited to consent to pharmacogenetics analyses, unless underlying causal mutations of HoFH are well documented by a validated specialized laboratory.

Efficacy assessments will include measurement of the effects of inclisiran on levels of LDL-C, other lipoproteins including total cholesterol (TC), triglycerides, high-density lipoprotein cholesterol (HDL-C), non-HDL-C, very low-density lipoprotein cholesterol (VLDL-C), apolipoprotein A1 (Apo-A1), apolipoprotein B (Apo-B), lipoprotein(a) [Lp(a)], and PCSK9.

Formation of anti-drug antibodies (ADA) will be assessed on Day 1 (prior to and 4 hours after the injection) and on subsequent visits until the end-of-study (EOS).

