^a Day 104 visit only for those subjects who receive a second dose of study drug. Dose #2 may be given at Day 90 or 104 depending on PCSK9 levels as compared to baseline

^b Vital signs: blood pressure and heart rate will be measured prior to injection and at 4 hours after injection. ^c ECG is performed prior to the injection on Day 1.

^d Hematology, chemistry (including lactate, bicarbonate, glucose, HbA1c, liver and renal function, hsCRP, IL6, IFN-γ, and TNF-α), and coagulation testing. Blood samples for determination of laboratory values will be performed prior to study drug injection where relevant. All laboratory testing will be performed with subjects in a fasted state.

^e Lab tests performed in participating institution's laboratory. Results must be available before the start of study drug injection on Day 1 to confirm subjects meet eligibility criteria.

^f Lab tests performed by study's designated Central Lab facility from enrollment to EOS. In addition, subjects in whom LDL-C reduction is less than 20% of the absolute reduction from baseline to Day 90 will continue to be followed up on a monthly visit schedule either until this level has been reached or until Day 300.

^g Urinalysis collection is prior to the injection on Day 1.

^h Urine pregnancy test performed at each visit for females of childbearing potential. In addition, postmenopausal women who are less than 55 years of age will have a pregnancy test within 24 hours of enrollment and prior to any study drug injection. Results must be available prior to the injection on Day 1 and, if a second dose of study drug is required, on Day 90/104.

ⁱ Females of childbearing potential will have a pregnancy test at each additional follow-up visit until LDL-C reduction is less than 20% of the absolute reduction from baseline to Day 90.

^j Two ADA samples will be drawn on Day 1: one before the injection and one 4 hours after the injection. ^k Additional aliquots of plasma and serum will be collected at each time point and stored for future analyses.

^l For subjects in whom LDL-C reduction is less than 20% of the absolute reduction from baseline to Day 90, formation of ADA will be assessed at the last visit. ^m Efficacy parameters (Lipids / lipoproteins) will include LDL-C, total cholesterol, triglycerides, HDL-C, non-HDL-C, very low-density lipoprotein (VLDL-C), apolipoprotein A1 (Apo-A1), apolipoprotein B (Apo-B), lipoprotein(a) [Lp(a)], and PCSK9.

ⁿ Day 270 only.

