^o Sample may be taken during screening or anytime during study to be processed and stored, but only after separate consent has been signed. ^p Additional Follow-Up visits only for those subjects in whom LDL-C reduction is less than 20% of the absolute reduction from baseline to Day 90.

^q 3 aliquots of plasma and 3 aliquots of serum will be stored for efficacy and safety biomarker analysis if needed. All samples will be destroyed 1 year following the last subject's last visit in the study.

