2.7. Assessment of Efficacy

Specimens for assays of lipids/lipoproteins will be obtained at the time points in the Schedule of Assessments ([Table 1](#)). Subjects will be in a fasted state for all efficacy laboratory assessments. Parameters to be assessed will include: total cholesterol (TC), triglycerides, LDL-C, HDL-C, non-HDL-C, very low-density lipoprotein (VLDL-C), apolipoprotein A1 (Apo-A1), apolipoprotein B (Apo-B), lipoprotein(a) [Lp(a)], and PCSK9.

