5.2. General Statistical Considerations and Definitions

5.2.1. General Statistical Methods

All study-collected data will be summarized by treatment group using descriptive statistics, graphs, and/or raw data listings. Categorical variables will be summarized using counts and percentages. Percentages are based on the number of subjects in the analysis set for whom there are non-missing data, unless otherwise specified. Continuous variables, including changes from day 1, will be summarized using descriptive statistics (n, mean, standard deviation [SD], median and interquartile range [first and third quartiles], minimum and maximum). All summaries are presented for all subjects due to the small sample size in this study.

The Statistical Analysis Plan (SAP) will be finalized before database lock.

Statistical analyses will be carried out using SAS statistical analysis software version 9.2 or higher (SAS Institute, Inc., Cary, North Carolina, USA).

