5.2.4. Missing data handling

Unless otherwise specified, missing data will not be imputed and will be excluded from the associated analysis.

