5.3.6. Efficacy Analysis

5.3.6.1. Primary Efficacy Endpoints

The primary endpoint is the percent change in LDL-C following 90 and 180 days of treatment.

Summary statistics and 95% CI of this primary endpoint will be provided. Changes of LDL-C from Day 1 by scheduled visits will also be summarized. Response rate of subjects with 15% or greater reduction in LDL-C from Day 1 following 90 and 180 days of treatment will be calculated.

The analysis for the primary endpoint will be descriptive. Means and confidence intervals will be provided. Mean plots with standard error bars will be provided for observed LDL-C value, change in LDL-C value, and percent change in LDL-C value.

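### Day 104 is attended only by re-dosed subjects but falls inside the all-subject visit means, so the LDL-C and PCSK9 time courses can show a change that is partly or wholly a change in who is measured

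*SAP*

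**What the plan says.** **Who attends.** Footnote a of SAP Table 1 (section 1.4; same text in Protocol 6.1) says: "Day 104 visit only for those subjects who receive a second dose of study drug". Dose 2 may fall on Day 90 or on Day 104, so attendees can include both kinds of subject.

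**What is measured.** SAP 2.7 says: "Specimens for assays of lipids/lipoproteins will be obtained at the time points in the Schedule of Assessments". Table 1 marks lipids/lipoproteins at FU4X, and footnote m counts PCSK9 among them.

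**How it is summarised.** SAP 5.3.6.1 says "Changes of LDL-C from Day 1 by scheduled visits will also be summarized" and adds "Mean plots with standard error bars will be provided for observed LDL-C value, change in LDL-C value, and percent change in LDL-C value". SAP 5.3.6.2 applies a similar analysis to LDL-C, PCSK9 and the other lipids at each visit up to Day 180 or the final visit. SAP 5.2.1 says "All summaries are presented for all subjects due to the small sample size in this study", and SAP 5.2.4 says "Unless otherwise specified, missing data will not be imputed and will be excluded from the associated analysis". Nothing exempts Day 104, splits subjects by second dose, or asks for n on the plots.

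**What triggers dose 2.** SAP 1.1 gives the condition as "if mean serum PCSK9 levels are not suppressed by > 70% at Day 60 or 90, as compared to baseline". SAP 2.3 and footnote a read as a decision for each subject.

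**After Day 180.** Footnote p of Table 1 says: "Additional Follow-Up visits only for those subjects in whom LDL-C reduction is less than 20% of the absolute reduction from baseline to Day 90". SAP 2.5 agrees. SAP 1.1 and 5.2.3 instead keep subjects in the study until the reduction has fallen below that level.

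**The concern.** Followed literally, the plan computes means from everyone at Day 90 and Day 120, and between them a mean from only those who received dose 2. Those subjects are picked out by their PCSK9 response. A reader of the table or curve would naturally take the Day 90 to Day 104 to Day 120 sequence as the course of one group.

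At stake are the secondary time courses. Protocol 1.3 says the study tests efficacy and duration of effect, and that it will allow dose selection for Phase III. An apparent loss or return of effect around the second dose bears on that purpose. The problem is most direct for PCSK9, because the plotted outcome is also the variable that decides who attends.

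**Working it through.** The documents state no figure to reproduce: there is no effect size, SD or expected number of re-dosed subjects. The check therefore isolates the part of any Day 104 shift that comes from composition alone.

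**1. Formula.** Let m of n subjects be re-dosed, with mean percent change in LDL-C *a* in the re-dosed and *b* in the others, and D = *a* − *b*. Hold every subject's value fixed between visits.
- All-subject mean = [m·*a* + (n − m)·*b*] / n
- Day 104 mean (attendees only, nothing imputed) = *a*
- Gap = *a* − [m·*a* + (n − m)·*b*] / n = (1 − m/n) × D

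**2. Inputs.** n = 8 to 10 (SAP 1.1). m and D are assumptions; the documents give neither.

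**3. Composition gap, percentage points**

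| n | m | 1 − m/n | D = 5 | D = 10 | D = 20 |
|---|---|---|---|---|---|
| 8 | 2 | 0.75 | 3.75 | 7.5 | 15 |
| 8 | 4 | 0.50 | 2.5 | 5 | 10 |
| 8 | 6 | 0.25 | 1.25 | 2.5 | 5 |
| 8 | 8 | 0 | 0 | 0 | 0 |
| 10 | 2 | 0.80 | 4 | 8 | 16 |
| 10 | 5 | 0.50 | 2.5 | 5 | 10 |
| 10 | 8 | 0.20 | 1 | 2 | 4 |
| 10 | 10 | 0 | 0 | 0 | 0 |

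As an example with assumed values, take n = 8 and m = 4, with others at −30% and re-dosed at −10% (D = 20). The all-subject mean is (4 × −30 + 4 × −10)/8 = −20%, the attendee mean is −10%, and the gap is 10 points with no change in any subject.

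**4. Chance composition.** Even if D is zero on average, the subgroup mean differs from the full mean by chance with SD = s × √(1/m − 1/n). With an assumed s = 15 points:
- n = 8, m = 4: 15 × √(0.25 − 0.125) = 5.3 points
- n = 10, m = 4: 15 × √(0.25 − 0.10) = 5.8 points

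On the observed-value plot, an assumed between-subject SD of 100 mg/dL gives 35 and 39 mg/dL for the same two cases. For equal SD, the standard error bar widens by √(n/m), which is 1.41 times at half attendance.

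**5. How often a mixed cohort arises.** A simulation of 40,000 trials per setting applied the 70% threshold to each subject. Assumptions: mean PCSK9 suppression 65, 70 or 75% with SD 10; LDL-C percent change SD 15; no within-subject change; correlation between PCSK9 suppression and LDL-C reduction of 0, 0.3 or 0.6.
- Some but not all subjects were re-dosed in 94.5–99.8% of trials.
- Among those trials the mean gap was about 0 at correlation 0, 2.4–5.1 points at 0.3 and 4.7–10.2 points at 0.6, towards less reduction.
- The gap exceeded 5 points in either direction in 13–78% of them.

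**6. What the formula leaves out.** Subjects dosed at Day 90 are sampled about 14 days after dose 2. Subjects dosed at Day 104 are sampled before that injection (Table 1, footnote d). A real drug effect in the first group is therefore added to the composition gap, and the net direction cannot be derived.

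**7. PCSK9.** If the threshold is applied per subject, re-dosed and other subjects differ in PCSK9 at the deciding visit by construction. By Day 104 the early re-dosed may have moved again, so direction is uncertain here too.

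**The case against.** A reader might infer that the plan will produce a false loss of LDL-C effect at Day 104 of 10 to 16 points. The documents do not support that, for four reasons.

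- **Partial re-dosing is not certain.** The trigger in SAP 1.1 is worded as a mean PCSK9 level. Applied to the cohort mean, all or none would be re-dosed, and Day 104 would be everyone or absent. This stands as an ambiguity. But footnote a and SAP 2.3 read subject by subject, and a visit reserved for some subjects anticipates a mixed cohort.
- **Size and direction are unknown.** The 10–16 points need D = 20. Selection is on PCSK9, and SAP 1.1 expects causal mutations to influence LDL-C response, so weak PCSK9 suppression need not mark weak LDL-C response. A response to a Day 90 dose could offset or reverse an upward shift. This stands for LDL-C. It does not make the Day 104 mean comparable with its neighbours.
- **Plotting Day 104 is the default reading.** SAP 5.3.6.1 does not list the plotted visits. The by-visit summary, however, has no exception.
- **Some protection exists.** SAP 5.2.1 puts n in every continuous summary, SAP 5.2.3 puts all data in listings, and SAP 5.3.4 lists dosing. With 8–10 subjects the change in attendance can be traced. But n alone does not show that attendance was selected, and the plots need not carry it.

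A reader might also infer a matching, known distortion at Days 210–300. Attendance there depends on LDL-C, but footnote p and SAP 2.5 select the opposite subjects from SAP 1.1 and 5.2.3. SAP 1.1 also calls Day 180 the last lipid estimation. Neither the direction nor whether visit means are planned there can be settled from the text.

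**Conclusion.** The point holds as a conditional one. If some but not all subjects are re-dosed, the Day 104 mean is a PCSK9-selected subgroup that mixes post-dose-2 and pre-dose samples. It should not stand in the same series as the all-subject Day 90 and Day 120 means.

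The LDL-C composition gap is (1 − m/n) × D. Its size rests wholly on the assumed D and m; the 2.5–16 point span covers D = 5 to 20 with 2–4 of 8 or 2–5 of 10 re-dosed. It vanishes if all are re-dosed, and its expectation is zero if D is zero. For scale, the Phase III benchmark in SAP 1.1 is a mean reduction of 15%.

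The primary endpoint (SAP 2.7.1) and the response rates (SAP 5.3.6.1) use Days 90 and 180 and are untouched. The effect is confined to descriptive by-visit tables and curves for LDL-C, PCSK9 and the other lipids. The change is worth making because it removes a composition bias at almost no cost.

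**What to change.** In SAP 5.3.6.1 and 5.3.6.2:

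- Leave Day 104 out of the all-subject visit means and mean plots.
- Tabulate Day 104 for re-dosed subjects only, beside the same subjects' Day 90 and Day 120 values, split by whether dose 2 was given at Day 90 or Day 104.
- Add individual-subject profiles, with dose 2 marked.
- Print n at every plotted visit.
- Treat any post-Day 180 visits the same way.

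Two sets of passages must also be reconciled. One is whether re-dosing is judged on a mean PCSK9 level (SAP 1.1) or per subject (Table 1 footnote a, SAP 2.3). The other is who attends after Day 180 (Table 1 footnote p and SAP 2.5 against SAP 1.1 and 5.2.3). The matching Protocol text should be aligned.

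The cost is SAP wording and one extra table or plot, with no new data. The composition artefact at Day 104 then disappears from the all-subject series by construction. What is given up is an all-subject Day 104 estimate, which the design cannot supply unless everyone is re-dosed.

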2. GENERAL CONDUCT OF TRIAL

Written informed consent will be obtained for this study by the principal investigator or sub investigator from all subjects before the performance of any protocol-specific procedure (if the subject is less than 18 years of age, written consent will be obtained from their guardian or legally authorized representative, with verbal assent from the child).

2.1. Screening Period (Days –28 to –1)

The following procedures will be performed within 28 days prior to enrollment:

All screening laboratory tests will be analyzed at the Central Lab, with the exception of urinalysis and pregnancy test, which will be done in-house at the participating institution's laboratory using the testing materials provided by the Central Lab. The results of all screening laboratory tests should be reviewed prior to enrollment. If these results confirm an exclusion criterion or suggest any contraindication to treatment with inclisiran, and/or other required ancillary medication(s), the subject must not be enrolled.

1. Review of inclusion/exclusion criteria to confirm subject eligibility.
2. Documentation of:
 - a. Demography: age, gender and ethnic origin
 - b. Medical history
 - c. Concomitant medications
3. Full physical examination including height, weight and full neurological examination (as described in Protocol Appendix A).
4. Vital signs (blood pressure and heart rate).
5. Blood samples drawn for screening clinical laboratory tests and results reviewed prior to enrollment. All laboratory testing will be performed with subjects in a fasted state.
 - a. Biochemistry
 - b. Inflammatory markers
 - c. Lipids/lipoproteins
 - d. Hematology
 - e. Coagulation
 - f. HbA1c
 - g. Biomarker (stored samples)
 - h. Pharmacogenetics (stored samples, only if separate consent has been signed)
6. Urinalysis (local), using standardized supplies from Central Lab.

Urine pregnancy test (local), using standardized supplies from Central Lab, for females of childbearing potential. In addition, postmenopausal women who are less than 55 years of age must have a negative pregnancy test within 24 hours of enrollment.

2.2. Enrollment (Day 1)

Enrollment should only occur once subject eligibility is confirmed.

The following procedures will be performed prior to the injection of study drug:

1. Review of inclusion/exclusion criteria
2. Vital signs (blood pressure and heart rate will be measured prior to injection and at 4 hours after injection)
3. 12-lead ECG
4. Blood samples drawn for clinical laboratory tests (Central Lab):
 - a. Biochemistry
 - b. Inflammatory markers
 - c. Lipids/lipoproteins
 - d. Hematology
 - e. Coagulation
 - f. HbA1c
 - g. Anti-inclisiran (ADA) antibodies (prior to and 4 hours after the injection)
 - h. Biomarkers (stored samples)
5. Urinalysis (local)
6. Urine pregnancy test (local), for females of childbearing potential. In addition, postmenopausal women less than 55 years of age will have a pregnancy test within 24 hours of enrollment. Results must be available prior to the first injection of study drug
7. Concomitant medications
8. AE reporting
9. SAE reporting
10. Enrollment (only after subject eligibility is confirmed)

If eligible, the subject will receive the first injection (SC) of study drug and will be observed in the clinic for at least 4 hours post-injection before being discharged. The site of injection is the abdomen. The injection site will be marked and mapped for later observation. The following procedures will be performed 4 hours after the injection:

11. Vital signs: blood pressure and heart rate
12. Blood samples drawn for Anti-inclisiran (ADA) antibodies
13. Concomitant medications
14. AE reporting
15. SAE reporting

2.3. Follow-up Visits FU 1-6

Subjects will return to the study center after study drug administration for Follow-Up Visits according to the Schedule of Events/Assessments ([Table 1](#)) until the end of the study. Procedures will be as follows:

1. Vital signs (blood pressure and heart rate will be measured prior to injection and at 4 hours after injection)
2. Blood samples drawn for clinical laboratory tests:
 - a. Biochemistry
 - b. Inflammatory markers
 - c. Lipids/lipoproteins
 - d. Hematology
 - e. Coagulation
 - f. HbA1c (only at Days 90 and 180 and Day 270 if applicable)
 - g. Anti-inclisiran(ADA) antibodies (only at Day 30 and Day 150)
 - h. Biomarkers (stored samples)
3. Urine pregnancy test (local) for females of childbearing potential. In addition, on Day 90 or 104 (if a second dose of study drug is required), postmenopausal women less than 55 years of age will have a pregnancy test and results must be available prior to the injection
4. Concomitant medications
5. AE reporting
6. SAE reporting
7. Study drug administration **ONLY** for subjects requiring a second dose of study drug (depending on the degree of suppression of serum PCSK9 as compared to baseline).

If a second dose is deemed necessary, the subject will receive the injection (SC) at **Day 90 or 104**, based on the PCSK9 levels from the previous visit. The site of injection is the abdomen (on the opposite side than the injection on Day 1). The injection site will be marked and mapped for later observation.

2.4. End of Study (EOS) Visit (FU 7)

A subject's participation in the study is complete when all procedures at the last study visit have been completed and all ongoing SAEs have been followed to resolution.

Procedures will be as follows:

1. Vital signs (blood pressure and heart rate)
2. Physical examination (including full neurological examination as described in protocol Appendix A)
3. 12-lead ECG
4. Blood samples drawn for clinical laboratory tests:
 - a. Biochemistry
 - b. Inflammatory markers
 - c. Lipids/lipoproteins
 - d. Hematology
 - e. Coagulation
 - f. Anti-inclisiran (ADA) antibodies

- g. Biomarkers (stored samples)
- 5. Urinalysis (local)
- 6. Urine pregnancy test (local) for females of childbearing potential
- 7. Concomitant medications
- 8. AE reporting
- 9. SAE reporting

2.5. Additional Follow-Up Visits (FU 8-11, if needed)

These visits are only for those subjects in whom LDL-C reduction is less than 20% of the absolute reduction from baseline to Day 90. Procedures will be as follows:

1. Blood samples drawn for clinical laboratory tests:
 - a. Biochemistry
 - b. Inflammatory markers
 - c. Lipids/lipoproteins
 - d. Hematology
 - e. Coagulation
 - f. HbA1c (only at Day 270)
 - g. Anti-inclisiran (ADA) antibodies (only at last visit)
 - h. Biomarkers (stored samples)
2. Urinalysis (local)
3. Urine pregnancy test (local). Females of childbearing potential will have a pregnancy test at each additional follow-up visit until LDL-C reduction is less than 20% of the absolute reduction from baseline to Day 90
4. Concomitant medications
5. AE reporting
6. SAE reporting

2.6. Assessment of Safety

2.6.1. Adverse Events

Subjects will be carefully monitored for adverse events by the investigator during the designated study period (See Section 3).

